APPENDIX C: Description of the iRECIST Process for Assessment of Disease Progression

Assessment at Screening and Prior to RECIST 1.1 Progression

Until radiographic progression based on RECIST 1.1, there is no distinct iRECIST assessment.

Assessment and Decision at RECIST 1.1 Progression

In participants who show evidence of radiological PD by RECIST 1.1 the Investigator will decide whether to continue a participant on study treatment until repeat imaging is obtained using the criteria outlined in Section 5.9.1.

If the Investigator decides to continue treatment, the participant may continue to receive study treatment and the tumor assessment should be repeated 4 to 8 weeks later to confirm PD by iRECIST, per Investigator assessment.

Tumor flare may manifest as any factor causing radiographic progression per RECIST 1.1, including:

- Increase in the sum of diameters of target lesion(s) identified at baseline to \geq 20% and \geq 5 mm from nadir
 - Please note: the iRECIST publication uses the terminology "sum of measurements", but "sum of diameters" will be used in this protocol, consistent with the original RECIST 1.1 terminology.
- Unequivocal progression of non-target lesion(s) identified at baseline
- Development of new lesion(s)

iRECIST defines new response categories, including **iUPD** (unconfirmed progressive disease) and **iCPD** (confirmed progressive disease). For purposes of iRECIST assessment, the first visit showing progression according to RECIST 1.1 will be assigned a visit (overall) response of iUPD, regardless of which factors caused the progression.

At this visit, target and non-target lesions identified at baseline by RECIST 1.1 will be assessed as usual.

New lesions will be classified as measurable or non-measurable, using the same size thresholds and rules as for baseline lesion assessment in RECIST 1.1. From measurable new lesions, up to 5 lesions total (up to 2 per organ), may be selected as New Lesions – Target. The sum of diameters of these lesions will be calculated, and kept distinct from the sum of diameters for target lesions at baseline. All other new lesions will be followed qualitatively as New Lesions – Non-target.

Assessment at the Confirmatory Imaging

On the confirmatory imaging, the participant will be classified as progression confirmed (with an overall response of iCPD), or as showing persistent unconfirmed progression (with an overall response of iUPD), or as showing disease stability or response (iSD/iPR/iCR).

Confirmation of Progression

Progression is considered confirmed, and the overall response will be iCPD, if ANY of the following occurs:

- Any of the factors that were the basis for the initial iUPD show worsening
 - \circ For target lesions, worsening is a further increase in the sum of diameters of ≥ 5 mm, compared to any prior iUPD time point
 - For non-target lesions, worsening is any significant growth in lesions overall, compared to a prior iUPD time point; this does not have to meet the "unequivocal" standard of RECIST 1.1
 - o For new lesions, worsening is any of these:
 - An increase in the new lesion sum of diameters by ≥ 5 mm from a prior iUPD time point
 - Visible growth of new non-target lesions
 - The appearance of additional new lesions
- Any new factor appears that would have triggered PD by RECIST 1.1

Persistent iUPD

Progression is considered not confirmed, and the overall response remains iUPD, if:

- None of the progression-confirming factors identified above occurs AND
- The target lesion sum of diameters (initial target lesions) remains above the initial PD threshold (by RECIST 1.1)

Additional imaging for confirmation should be scheduled 4 to 8 weeks from the scan on which iUPD is seen. This may correspond to the next visit in the original visit schedule. The assessment of the subsequent confirmation scan proceeds in an identical manner, with possible outcomes of iCPD, iUPD, and iSD/iPR/iCR.

Resolution of iUPD

Progression is considered not confirmed, and the overall response becomes iSD/iPR/iCR, if:

- None of the progression-confirming factors identified above occurs, AND
- The target lesion sum of diameters (initial target lesions) is not above the initial PD threshold.

The response is classified as iSD or iPR (depending on the sum of diameters of the target lesions), or iCR if all lesions resolve.

In this case, the initial iUPD is considered to be pseudo-progression, and the level of suspicion for progression is "reset". This means that the next visit that shows radiographic progression,

whenever it occurs, is again classified as iUPD by iRECIST, and the confirmation process is repeated before a response of iCPD can be assigned.

Detection of Progression at Visits After Pseudo-progression Resolves

After resolution of pseudo-progression (i.e., achievement of iSD/iPR/iCR), iUPD is indicated by any of the following events:

Target lesions

O Sum of diameters reaches the PD threshold ($\geq 20\%$ and ≥ 5 mm increase from nadir) either for the first time, or after resolution of previous pseudo-progression. The nadir is always the smallest sum of diameters seen during the entire trial, either before or after an instance of pseudo-progression.

Non-target lesions

- o If non-target lesions have never shown unequivocal progression, their doing so for the first time results in iUPD.
- o If non-target lesions had shown previous unequivocal progression, and this progression has not resolved, iUPD results from any significant further growth of non-target lesions, taken as a whole.

New lesions

- o New lesions appear for the first time
- Additional new lesions appear
- o Previously identified new target lesions show an increase of ≥ 5 mm in the new lesion sum of diameters, from the nadir value of that sum
- o Previously identified non-target lesions show any significant growth

If any of the events above occur, the overall response for that visit is iUPD, and the iUPD evaluation process (see Assessment at the Confirmatory Imaging above) is repeated. Progression must be confirmed before iCPD can occur.

The decision process is identical to the iUPD confirmation process for the initial PD, except in one respect. If new lesions occurred at a prior instance of iUPD, and at the confirmatory scan the burden of new lesions has increased from its smallest value (for new target lesions, their sum of diameters is ≥ 5 mm increased from its nadir), then iUPD cannot resolve to iSD or iPR. It will remain iUPD until either a decrease in the new lesion burden allows resolution to iSD or iPR, or until a confirmatory factor causes iCPD.

Additional details about iRECIST are provided in the iRECIST publication²⁰.

Table 6: Comparison between RECIST 1.1 and iRECIST

	RECIST 1.1	iRECIST	
Definitions of disease: numbers, sites and target or non	Measurable are diameters greater than 10 mm (15 for nodes maximum of 5 (2 per organ)	No change from RECIST 1.1	
CR, PR or SD	Cannot have met criteria for progression	Can have had iUPD (more than once) but not iCPD before iCR, iPR or iSD	
Confirmation of CR or PR	Only in non-randomized studies	As per RECIST 1.1	
Confirmation of SD	Not required	As per RECIST 1.1	
New lesions	Progression: recorded but not measured	iUPD but only becomes iCPD if on the next scan there are new lesions or the size increases by greater than 5 mm	
Confirmation of progression	Not required	Required	
Consideration of clinical status	Not required	Clinical stability considered at iUPD to decide treatment continuation	

Table 7: Trajectory of progression in iRECIST

Target Lesions: iCR, Non-target: iCR, no new lesions	iCR	iCR
Target lesions: iCR, Non- target: non iCR/non iUPD, no new lesions	iPR	iPR
Target Lesions: iPR, Non- target: non iCR/non iUPD, no new lesions	iPR	iPR
Target lesions: iSD, Non- target: non iCR/non iUPD, no new lesions	iSD	iSD
Target lesions: iUPD with no change or with a decrease from the last time point, Nontarget: iUPD with no change or decrease from last time point, new lesions	NA	New lesions confirm iCPD if new lesions previously identified and increased in size (≥ 5 mm in sum of measures for new lesions or any increase for new lesion non-target) or increase in number. If no change is seen in new lesions assignment remains iUPD
Target lesions: iSD, iPR, iCR, non-target: iUPD, no new lesions	iUPD	Remains iUPD unless iCPD is confirmed by increase in the size of non-targets (does not need to meet RECIST 1.1 criteria)
Target lesions: iUPD, non-target: non iCR/non iUPD, no new lesions	iUPD	Remains iUPD unless iCPD confirmed on the basis of further increase ≥ 5 mm; otherwise stays as iUPD
Target lesions: iUPD, non-target: iUPD, no new lesions	iUPD	Remains iUPD unless iCPD confirmed on previously identified targets iUPD ≥ 5 mm or non-target iUPD
Target lesions: iUPD, non-targets: iUPD, new lesions	iUPD	Remains iUPD unless iCPD confirmed by increase of ≥ 5 mm previously identified target, or non-target or an increase in size or number of new lesions
Target lesions non iUPD or progression, non-targets: non iUPD or progression, new lesions	iUPD	Remains iUPD unless iCPD confirmed by increase in size or number of new lesions previously identified.

Target lesions, non-target lesions and new lesions are defined according to RECIST 1.1 criteria: if no pseudoprogression occurs, RECIST 1.1 and iRECIST categories for CR, PR and SD are the same. * Previously identified in the assessment prior to this time point. 'I' indicates immune responses assigned using iRECIST

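### Appendix C text and Table 7 classify the same unchanged confirmatory scan differently when iUPD came only from new lesions or only from non-target progression, so the exploratory iRECIST endpoints have no single scoring rule

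*Combined protocol and SAP*

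**What the plan says.** Under Appendix C, the first visit with RECIST 1.1 progression "will be assigned a visit (overall) response of iUPD, regardless of which factors caused the progression". A new lesion alone, or non-target progression alone, is therefore enough.

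At the confirmatory scan, if no confirming factor is present, two subsections of the text decide the outcome. *Persistent iUPD* applies if the sum of the initial target lesions is still above the PD threshold. *Resolution of iUPD* applies if "The target lesion sum of diameters (initial target lesions) is not above the initial PD threshold". On resolution, "The response is classified as iSD or iPR (depending on the sum of diameters of the target lesions), or iCR if all lesions resolve". The text adds: "In this case, the initial iUPD is considered to be pseudo-progression". Suspicion is then reset, and the next progression starts again as iUPD.

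Table 7 has a row for each of the two situations in question:

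- Targets in iSD, iPR or iCR, non-targets in iUPD, no new lesions: "Remains iUPD unless iCPD is confirmed by increase in the size of non-targets".
- Neither targets nor non-targets in progression, new lesions present: "Remains iUPD unless iCPD confirmed by increase in size or number of new lesions previously identified".

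Sections 1.3.3 and 11.3 list DCR, ORR, PFS and DOR by iRECIST as exploratory. Sections 11.1, 11.2 and 13.2 base the primary DCR and the secondary ORR and PFS on RECIST 1.1, with documented clinical progression also counting for PFS.

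**The concern.** The text looks only at the target sum when it decides whether iUPD has gone away. If the target sum did not cause the iUPD, that test says nothing about the lesion that did. A stable new metastasis would then be read as iSD under the text and as iUPD under Table 7.

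Two readers could each follow Appendix C and record different categories for identical measurements. The iRECIST endpoints would depend on which part of the appendix was used. If this is not settled in advance, the choice could be made after the results are known.

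**Working it through.** No published figure is at issue, so the check compares two sets of rules. Table 7's column headings are missing from the text available to me. I take the last column to apply to patients with a prior iUPD, because its entries speak of remaining iUPD.

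**Rules at the confirmatory scan, with no worsening and no new factor**

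- Text: iUPD if the target sum is above the PD threshold. Otherwise iSD or iPR by target sum, or iCR only if all lesions have resolved.
- Table 7: every row that yields iSD, iPR or iCR requires no new lesions and non-targets not in iUPD. The two rows quoted above stay at iUPD unless the lesions concerned grow or, for new lesions, increase in number.

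**All combinations with an unresolved trigger**

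| Target status | What persists unchanged | Text | Table 7 |
|---|---|---|---|
| iSD | new lesion only | iSD | iUPD |
| iSD | non-target only | iSD | iUPD |
| iPR | new lesion only | iPR | iUPD |
| iPR | non-target only | iPR | iUPD |
| iCR | new lesion only | iPR | iUPD |
| iCR | non-target only | iPR | iUPD |
| iSD, iPR or iCR | both (3 combinations) | iSD, iPR, iPR | no row; iUPD by extension |
| above PD threshold | with or without the others (4 combinations) | iUPD | iUPD |

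The iCR lines show iPR under the text because it offers only iSD or iPR while other lesions remain. The rules disagree in all 6 combinations that have an explicit Table 7 row, and in 3 more by extension. They agree in all 4 combinations with the target sum above the threshold.

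**Worked case (illustrative measurements)**

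1. Baseline target sum 60 mm. Week 8: 60 mm plus a new 12 mm liver lesion. Both rules give iUPD.
2. Week 16: 60 mm, new lesion still 12 mm. The text gives iSD with a reset; Table 7 gives iUPD.
3. If instead the week-16 target sum is 40 mm, the decrease is (60 − 40)/60 = 33.3%, which passes the 30% needed for partial response. The text gives iPR; Table 7 gives iUPD.
4. If the new lesion then grows by at least 5 mm, the text records a fresh iUPD that needs confirmation. Table 7 records iCPD, because the patient never left iUPD. iRECIST PFS and DOR can therefore differ too.

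**Does another part of the appendix settle it?** No.

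- The rules for visits after pseudo-progression resolves cover non-target progression that is still unresolved. The text therefore does expect resolution while a trigger persists.
- The same subsection bars resolution because of new lesions only when their burden has risen from its smallest value. It presents this as the one difference from the process for the initial progression. An unchanged lesion at the first confirmatory scan is not covered.
- Table 6 says when a new lesion makes the reading iCPD, but not what an unchanged one becomes.
- The reference to the iRECIST publication for further detail sets no order of precedence.

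**Scale.** Section 13.1 targets 21 evaluable patients. If iRECIST DCR used that denominator and iUPD did not count as disease control (both assumptions), one reclassified patient would move it by 1/21 = 4.8 percentage points. With all 25 planned enrolments as denominator, the figure is 1/25 = 4.0 points.

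**The case against.** The strongest reply is that nothing decisive depends on this. The Simon rule, the primary DCR, the secondary ORR and PFS and the toxicity stopping rule use no iRECIST category. That stands, and it limits the point to exploratory results.

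The affected group is also narrow. The patient must have no target progression, must be treated on under Section 5.9.1 without clinical deterioration, and must show no growth that would make the scan iCPD. Section 12.3 has the IND sponsor and site investigators confirm response assessments. That may reduce inconsistent reads, but it does not tell them which rule to apply.

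Four stronger readings are tempting, and the documents do not support them:

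- *The text biases the iRECIST results upward by calling real progression pseudo-progression.* This presumes that Table 7 is right. The text is a developed scheme that allows resolution while other lesions persist, and nothing ranks the table above it.
- *Two or three patients would be affected, or 9.5 to 14.3 points, at the 4-month reading.* No patient count can be derived from the documents. Sections 1.3.3 and 11.3 give iRECIST DCR no time point or denominator and do not say how iUPD counts. A first iUPD at week 8 is re-read at weeks 12 to 16, but one at week 16 is re-read at weeks 20 to 24.
- *Table 7's statement that "If no change is seen in new lesions assignment remains iUPD" is further evidence of conflict.* That row has target and non-target lesions both in iUPD, and with the target sum still above the threshold the text also gives iUPD.
- *iUPD should resolve only once every trigger has disappeared.* The post-resolution subsection lets a decrease in new-lesion burden permit resolution, so this rule would create a new contradiction unless that wording also changed.

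**Conclusion.** The contradiction is real and confined. It arises when iUPD was caused only by new lesions or only by non-target progression, the target sum is not above the PD threshold, and nothing has worsened. The text then gives iSD or iPR with a reset, and Table 7 keeps iUPD. The documents do not say which prevails.

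The consequence is limited to exploratory iRECIST DCR, ORR, PFS and DOR. The 4.8-point figure is a per-patient scale that rests on the two stated assumptions; it is not an estimate of the actual effect. The effect on iRECIST PFS and DOR cannot be sized, because the plan does not say which date counts as the iRECIST event. The conclusion is that text and table must be reconciled. The documents do not establish which of them is correct.

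**What to change.** Before any iRECIST results are analysed, adopt one scoring rule and amend these parts of Appendix C together so that they agree:

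1. *Persistent iUPD* and *Resolution of iUPD*.
2. The rules on post-resolution visits and new-lesion burden in *Detection of Progression at Visits After Pseudo-progression Resolves*.
3. Table 7, including a new row for targets not in iUPD with both non-target iUPD and new lesions.

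If Table 7 is adopted, make resolution depend on the status of the factors that triggered iUPD, not on the target sum alone. The wording on decreased new-lesion burden and on unresolved non-target progression must then be revised to match. If the text is adopted, change the two Table 7 rows.

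Re-score any iUPD follow-up scans already read by the chosen rule. The cost is a short amendment to one appendix and minor re-scoring from lesion assessments already recorded. If Table 7 is adopted, iRECIST DCR and ORR may be slightly less favourable.

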APPENDIX D: SAE Reporting Form

Serious Adverse Event Reporting Form

Please notify: [name] within 24 hours	
Incyte within 24 hours (email:	

Protocol Title:	A Phase II trial of retifanlimab (INCMGA00012) in patients with previously							
	treated unresectable or metastatic adenosquamous pancreatic or ampullary							
Protocol #: I-0012-19-07 J19106	Cancer Princip	oal Investig	gator:	Signature of PI:			Date:	
Report Type: Initial Follow-up Final Follow-up Death	Serious Criteria (check all t Death Life-threatening Hospitalization or Elongation o Other Important Medical Event		on of Hospitalization	Admiss: of Hospitalization		Date Event Discovered:		
Addendum to:	Canc Over	dose			Hospit Discha	al rge Date:	SAE ID:	
Section A: Subje	ct Infor	mation	~					
Subject ID:			Subject Male			Subject A	ge:	
Section B: Event	Inform	ation						
Event diagnosis symptoms:	or	Event Gra	ade:	Cause of deat (if applicable)		Event Out Not Rec Recover Recover Death Unknow	overed ing red red with sequelae	
Event Onset Dat	e (or Da	te of Death	ı):	Event End Da	Event End Date:			
Section C: Study	Drug I	nformation	1					
Investigational Product: Retifanlimab (500mg, IV, Q28 days)								
Indication: Previous cancer	Indication: Previously treated unresectable or metastatic adenosquamous pancreatic or ampullary cancer				or ampullary			

Number of Total Doses Give	Action taken with the study drug:					
Date of First Dose:	Date of Last Dose prio	□ None □ Interrupted □ Delayed □ Discontinued				
Relationship to:	Retifanlima	b	Underlying Disease			
Unrelated						
Related						
Section D: Brief Description	on of the Event:	•				
Section E: Relevant Tests/ Section F: Relevant Medic	·					
Section G: Concomitant D	rug (Not related to SA	(E)				
Name of the Drug	Start Date	Stop Date	Route	Dose	Frequency	
				 		
Section H: Comments						
Additional Documents:	Please specify
